The Effects of Dual Task Training on Motor and Non-Motor Function in Individuals with Parkinson's  
Disease

NCT02538029

9.6.16

**Rationale and Impact:** Activities of daily living often require the ability to dual task (DT), or simultaneously perform two attention-demanding motor or cognitive tasks. The ability to perform DT activities, in particular tasks that require a level of postural stability, is a fundamental problem for individuals with Parkinson’s disease (PD). Under DT constructs, individuals with PD typically exhibit a “posture second” strategy, where inadequate attention is allocated to gait and postural stability when challenged with a secondary task. In contrast, young and healthy older adults exhibit a “posture first” strategy by prioritizing gait and balance over the cognitive task. The “posture second” prioritization observed in PD may be a result of decreased attentional flexibility; thus when two tasks require concomitant attention, individuals with PD do not have the attentional flexibility to simultaneously attend to both tasks while controlling for motor deficits due to basal ganglia pathology. Hence, DT situations lead to increased loss of balance and falls in the PD population compared to their age-matched healthy peers. While these DT deficits in individuals with PD have been noted throughout the literature, there is a fundamental gap in understanding if DT deficits can be minimized through a behavioral intervention.

Single task (ST) training, defined as performing a motor or cognitive task in isolation, does not improve DT performance. DT deficits can be minimized in older adults through DT exercise interventions, which range from seated exercises to treadmill training with concurrent cognitive tasks. Several studies noted improvements in gait speed during DT constructs after DT specific training. DT training programs have also demonstrated the ability to improve spatiotemporal characteristics of gait, cognitive performance, clinical measures of balance, and quality of life measures in older adults with a history of falls. These DT therapeutic approaches have not been systematically evaluated in PD patients.

Individuals with PD demonstrate deterioration in stride length, step width, step variability, and walking speed in DT situations compared to performing walking alone. Although the literature is sparse, the feasibility of implementing a DT training program has been investigated for individuals with PD, with results indicating efficacy through improvements in gait speed during DT conditions, however, changes in non-motor outcomes have not been well documented. Additionally, it is not known how specific cognitive constructs affect gait. Stegemoller and colleagues suggested that cognitive processing speed correlated with stride length and walking speed, executive function correlated with step length variability, and that there were no significant associations with working memory for individuals with PD. However, these individuals performed the gait testing and cognitive testing separately, so it is not known what occurs when these tasks are performed simultaneously.

Biomechanical systems, such as virtual reality (VR) training, used to assess and treat gait deficits and concomitantly provide a secondary motor or cognitive are promising treatment interventions for individuals with PD. We propose that VR training may offer insight into the mechanism of DT deficits. [name] lab owns the one of two non-military installation of the Computer Assisted Rehabilitation Environment (CAREN), a VR reality system with a fully integrated 3-D motion capture system, a surround projection screen, dual belt treadmill with 6 degrees of freedom movable platform, two force platforms, a safety harness, and programmable software that can be used to create a variety of interactive modules (Figure 1). The interactive modules create either game-like or real-world environments that allow therapists to challenge the participant by altering either motor demands (e.g. virtual curbs, variations in walking

Figure 1: Module of wooded path on CAREN system. The treadmill (outlined in red) in front of the projection screen allows the individual feel like they are part of the scene.

surface, uneven surfaces) or cognitive demands (e.g. memory, attention, executive function) in a safe environment. The CAREN system is unique from other experimental environments due to the ability to create real-world environments (e.g. street scene with pedestrian and vehicle traffic, trail walking) in which the motor and cognitive aspects of function can be systematically manipulated and measured.

One of the greatest barriers to DT training is the lack of knowledge about effective clinical interventions. The clear benefit to this highly-advanced system is opportunity to investigate mechanisms of dual tasking deficits in a given environment. For example, if participants with PD exhibit increased step variability and decreased stride length during visual memory cognitive tasks that are not seen during verbal memory cognitive tasks, this would provide valuable insight into task selection during a clinical intervention.

**The primary aim of the proposed project is to characterize DT deficits to improve motor, cognitive, and quality of life outcomes in individuals with PD.** A single center study is outlined in Figure 2. Phase 1 of the intervention will involve an in-depth gait analysis on 15 individuals with PD. The purpose of Phase 1 is to generalize characteristics of gait and postural control during specific DT conditions, as in the example provided above. Phase 2 (N=20) involves the clinical translation of these findings. This phase will involve creating a clinical intervention based on the objective information gathered from the CAREN system. Researchers will use the biomechanical data gathered from the CAREN system to prioritize interventions based on given gait and postural control deviations during DT interventions. To continue with the above example, if we find that visual memory tasks lead to decreased stride length, then the therapeutic intervention would be a task such as targeted stepping during gait (e.g. placing stickers slightly wider than normal step length on a treadmill) while performing various visual memory tasks. The intervention will take place 3x/week for a total of 8 weeks. Interventional groups will include: 1) DT clinical group (N=10) and 2) Single task group (N=10). ST training will serve as a control group.

### **Specific Aims:**

#### **Aim 1: To categorize gait and balance deficits during DT constructs in individuals with PD.**

A three-dimensional (3-D) gait analysis using the CAREN system will be used during ST (walking alone) and DT conditions which consist of walking and completing tasks in the following cognitive domains: processing speed, visual memory, verbal memory, executive function, and attention (See Table 1 for cognitive tasks). Specifically, the CAREN gait analysis will examine spatiotemporal parameters of gait along with gait variability and joint angles. Additionally, a limit of stability (LOS) test will be conducted during ST and DT conditions.

*Hypothesis:* Gait parameters and LOS will be impaired under DT conditions compared to ST.

#### **Aim 2: To create and pilot a DT clinical intervention based on biomechanical analysis from the CAREN system that improves motor and non-motor function of individuals with PD.**

Primary motor outcome will include a 3-D gait analysis using the same parameters as stated in Aim 1. Secondary clinical motor outcome include distance walked during the 2 Minute Walk Test (2MWT) under ST and DT conditions. The Quality of Life in Neurological Disorders (Neuro-QOL) questionnaire will be administered as a quality of life measure. Fall risk will be assessed through the Activities-specific Balance Confidence (ABC) Scale. Cognitive measures, motor, and non-motor tests are described in Table 1.

*Hypothesis:* The DT clinical group will demonstrate the greater improvements in motor and non-motor function compared to the ST groups.

**Research Plan:** A total of 15 individuals diagnosed with idiopathic PD will be included in the initial gait analysis to categorize gait and postural control deficits associated with DT constructs (Figure 2). During Phase 1, all interventions will be carefully documented in order to attribute changes in gait parameters of postural stability with a domain of cognitive function. Phase 2 of the study (N=20) will randomize participants into two groups: 1) DT clinical and 2) ST (Figure 2). *Both groups will receive a time-matched intervention, 3x/week for a total of 8 weeks.* If an individual misses a session, he/she will be required to make it up on a different day of the same week or at the end in order for all 24 sessions to be complete. The entire intervention must be completed within a 10 week period. Intervention sessions for all groups will be completed under the guidance of a physical or occupational therapist who specializes in neurological rehabilitation. Outcome measures for Phase 2 will be administered at baseline, end of treatment (EOT), and EOT+4 weeks (EOT+4) by a blinded evaluator. The purpose of the EOT+4 testing is to gauge the permanence of the training intervention. All participants will be asked to wear a wrist-worn activity monitor that will measure steps/day throughout the duration of Phase 2 participation (baseline through EOT+4).

Motor, cognitive, and quality of life measures selected are described in Table 1. The Movement Disorder Society - Unified Parkinson's disease Rating Scale (MDS - UPDRS) will be taken at the beginning of both Phase 1 and 2 for demographic data. **Notably, cognitive tasks that are used for baseline and EOT evaluation will NOT be used during the intervention to ensure that a learning effect is not present.** Participants will take their PD medication as prescribed for all testing and interventions. If a participant has a life event (vacation, doctor's appointment, etc.) where they must miss a session, they will be permitted to make up the session. The total intervention duration cannot exceed 12 weeks from the date of the first intervention session.

**Dual Tasking Clinical (DT clinical):** Upon completion of Phase 1 of the study, a protocol for DT clinical training will be created based on the interventional gait analyses during various DT conditions. The DT clinical group will train in a traditional clinical rehabilitation environment. A variety of motor-cognitive or motor-motor tasks will be administered during balance and gait training (treadmill or over ground). Cognitive tasks will include processing speed, attention, memory, cognitive flexibility, and executive function tasks. Depending on the results of Phase 1, examples of a motor-cognitive tasks involving verbal memory may include recounting what he/she ate for breakfast this morning while navigating an obstacle course. Tasks will be graded based on the participant's baseline level of motor and cognitive function. The purpose of this group is to determine if a clinical

[figure not shown]

Figure 2: Study Flow Chart

intervention based on a biomechanical outcome is feasible and efficacious. The intervention will last approximately 45 min.

Single Task (ST): For this 45 minute session, individuals will perform 1) motor tasks; 2) cognitive tasks. An equal amount of time will be spent on the motor and cognitive tasks. Each task will be performed in a ST construct, where the participant will only have to focus on one task at a given time. Examples of ST motor include walking, static and dynamic balance activities such as single-leg stance or tandem stance, and reaching in various planes. Cognitive tasks will be administered with the participant in a seated position and include the same cognitive domains: processing speed, visual memory, verbal memory, executive function, and attention.

Table 1: Outcome Measures	
Outcome Measure	Function Evaluated
Motor Outcomes	
CAREN 3-D gait analysis during ST and DT (listed below) conditions to capture spatiotemporal gait characteristics	Objective quantification of gait during ST and DT conditions (e.g. step length, gait speed, step variability, kinetic and kinematic analysis and evaluation of ground reaction forces).
N-back test	Executive function, attention, and visual memory: participant is presented with a visual sequence of letters and is required to confirm the letter that is from N steps earlier in the sequence.
Stroop test	A measure of information processing speed; the participant is required to name the color that the word is printed, not the word itself. E.g. BLUE The correct response is red.
Repeating digit sequence	Verbal memory; participant is asked to repeat a string of increasingly longer digits
Serial 7s and arithmetic problems	Mathematical reasoning
Verbal fluency	Naming as many words as possible beginning with the letter “x”
2 Minute Walk Test (2MWT) under ST and DT conditions 1. ST walking only 2. DT Motor-Cognitive: 2MWT while performing serial 7 countdown 3. DT Motor-Motor: 2MWT while holding a cup of water $\frac{3}{4}$ full	Clinical measure of walking endurance both during isolated walking and during DT conditions; iPad will be worn on a belt on the back to capture asymmetry and sway
Limits of stability (LOS) test in the CAREN system (Phase 1)	Measure of postural control that quantify the maximum distance an individual can displace their center of mass within their base of support
Steps per day	Measure of physical activity behavior
Non-motor Outcomes	
Quality of Life in Neurological Disorders (Neuro-QOL) questionnaire	Quality of life measure specific to PD

Activities-specific Balance Confidence (ABC) Scale	Measure of confidence performing various activities without loss of balance or falls; predictive of recurrent falls
Cognitive measures performed during DT training and in a seated position	Measures cognitive function with and without (in a seated position) the coupling motor task
Tests using an iPad	Assessing information processing, vision, and balance
Questionnaires	Assessing falls, physical activity behavior, and quality of life

**Expected Results:** We anticipate that both DT and ST groups will improve motor and cognitive constructs in ST conditions. It is anticipated that the DT clinical group will improve compared to the ST group in both motor and cognitive performance during DT conditions, quality of life, and fall risk. We do not anticipate that DT constructs will change as a result of ST training due to specificity of training. We anticipate that one of the hallmark findings of this study will be insight to which DT constructs result in specific gait and postural control changes. This will guide clinicians in selecting the most appropriate interventions for individuals with PD, and we anticipate this to be the most important findings of this study to guide future research and clinical decisions.

**Participant Screening:** Participants will be pre-screened by the study coordinator. The following inclusion/exclusion criteria will be used:

Inclusion Criteria:

1. Clinical diagnosis of idiopathic PD
2. Able to provide informed consent
3. Ability to ambulate  $\geq 300$ ft with or without an assistive device
4. Hoehn and Yahr stage 2-4
5.  $\geq 2$  fall related to PD in the past 12 months

Exclusion Criteria:

1. Undergone any surgical procedure for the treatment of PD, such as deep brain stimulation
2. Those who have more than 2 uncontrolled cardiovascular risk factors (uncontrolled heart disease, uncontrolled diabetes, etc.) that would qualify them as a high risk exerciser
3. Musculoskeletal injury or neurological injury other than PD that would restrict physical activity
4. Inability to follow 2 step commands
5. Significant cognitive impairment as designated by  $\geq 3$  errors on the Short Portable Mental Status Questionnaire

**Impact on living well with Parkinson's disease:** From a patient perspective, successful DT performance is required to complete most activities of daily living (e.g. looking both ways while crossing a street and processing information related to the environment, holding a conversation while completing activities of daily living, driving a car in an unfamiliar environment, etc.) and is associated with falls, thus a DT deficit has a direct impact on quality of life. Currently, there is uncertainty whether rehabilitation specialists should incorporate DT training into a therapeutic exercise program, or if clinicians should avoid instructing individuals with PD to simply try to avoid DT activities during activities of daily living. The latter approach is not only impractical but would potentially lead to greater isolation for PD patients, which has been shown to have a significant impact on quality of life. A more empowering and sustainable approach is to better understand the DT declines and develop targeted intervention strategies to overcome these declines. The benefits of the DT interventions proposed are that they can be administered over a relatively short time period (conductive

for third party insurance payment) that is feasible in a clinical setting, and it can be modified by the results from high tech (VR) setting.

**Novel Aspects of this Project:** DT interventions are novel therapeutic interventions for PD. There are no studies that have examined DT interventions with the same rigor as proposed. This prospective, randomized study using a ST group as a time-matched control intervention has the potential to directly impact therapeutic treatment of individuals with PD. In addition, the VR intervention is novel technology that has the potential to capture more objective, biomechanical information. If biomechanical data gathered from the CAREN system is able to assist clinicians more appropriately select the ideal intervention, this could have an immediate impact on the way that DT is treated in individuals with PD.

**Data Confidentiality:** Study data that will be collected on the CAREN system will be de-identified using only the participant's study number. For purposes of the 3-D motion analysis, participants are videotaped; however this video will not leave the computer of the CAREN system without further written consent from the participant. Other outcome measures will be collected on Redcap®, a secure electronic database, where only research study personnel listed on this study submission will have access to the study data. Other electronic data will be labeled with only the subject number. The original signed and dated informed consent document along with any paper that may be used for data collection will be maintained in a study binder in a locked storage closet within [name] dedicated laboratory space in the Walker Building. The regulatory binder for this study will be kept in this same location, and only research personnel listed on this study submission will have access to this information.

**Potential Risks:** There are potential risks and discomforts to this study. There is a risk of muscle soreness and fatigue that comes along with exercising. There is a risk of falls in the clinical and VR setting, although in the VR setting participants will wear a harness to prevent falls. With the markers that will be worn for the gait analysis, there is a risk of temporary skin irritation. Although the intensity of exercise will be low, there is a risk of a cardiovascular event. All exercise personnel will be CPR certified and there is a medical emergency team located on site. There may be other risks with this intervention that are not yet known.

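### The rule keeping evaluation tasks out of training covers only cognitive tasks, so the plan leaves the DT arm alone free to practise the cup-carrying walk, one condition of a secondary outcome

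*Protocol*

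**What the plan says.** The Research Plan sets a safeguard, in bold type: "cognitive tasks that are used for baseline and EOT evaluation will NOT be used during the intervention". It gives the purpose in the same sentence: "to ensure that a learning effect is not present".

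The section on the DT clinical arm describes its training: "A variety of motor-cognitive or motor-motor tasks will be administered during balance and gait training (treadmill or over ground"). It neither lists nor excludes any motor task. The detailed programme comes later: "a protocol for DT clinical training will be created based on the interventional gait analyses during various DT conditions".

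The section on the Single Task arm says that "the participant will only have to focus on one task at a given time".

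On outcomes, Aim 2 says: "Secondary clinical motor outcome include distance walked during the 2 Minute Walk Test (2MWT) under ST and DT conditions". Table 1 gives three 2MWT conditions: walking only, walking with a serial-7 countdown, and "DT Motor-Motor: 2MWT while holding a cup of water". The primary motor outcome is the CAREN gait analysis with the parameters of Aim 1, which defines "DT conditions which consist of walking and completing tasks in the following cognitive domains".

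**The concern.** The protocol treats practice on an evaluation task as a threat to interpretation and writes a rule against it. For the motor-motor 2MWT that rule has nothing to act on, because the secondary task there is holding a cup. Only one arm's training can include such a combination, and it is the arm expected to do better.

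What is at stake is the meaning of one result. Expected Results predicts that the DT arm will gain over the ST arm in dual-task performance, and that ST training will not change dual-task constructs because training is specific. On that same reasoning, sessions spent walking with a cup of water would raise the cup-walk distance without showing that dual-tasking had improved more broadly. A reader of the results could not tell the two apart.

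**Working it through.** The documents give no power, SD or effect size, so there is no planned figure to reproduce. The check is mainly a comparison of the text.

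**1. Which evaluation tasks does the rule cover?**

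| Phase 2 outcome condition | Secondary task | Covered by the rule? |
|---|---|---|
| CAREN gait, dual-task (primary) | Cognitive (Aim 1) | Yes |
| 2MWT, walking only | None | Not applicable |
| 2MWT, serial-7 countdown | Cognitive | Yes |
| 2MWT, holding a cup of water | Motor | No |

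One condition is left uncovered: one of three 2MWT conditions, and one of the two dual-task ones.

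**2. Which arm could train it?** The DT arm does motor-motor tasks during gait training, over ground or on a treadmill, so walking with a cup fits its description. The ST arm does one task at a time, so it does not. Plain walking differs: it is among the ST arm's motor examples and is also part of the DT arm's gait training, so the walking-only 2MWT has no comparable imbalance between arms.

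**3. Does anything else close the gap?**
- The blinded evaluator (Research Plan) protects scoring but does not remove a practice effect.
- Time-matching (24 sessions in each arm) equalises the amount of training, not its content.
- The SAP's Phase 2 models contain group, time, their interaction and a random intercept. None of these separates practice on the test from a wider gain.
- The documents specify no Phase 2 record of which tasks were trained. The careful documentation described in the Research Plan concerns Phase 1.

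**4. Do the documents say that the cup walk will be trained?** No. The task list is to be written after Phase 1, and the one worked example in the DT section is motor-cognitive.

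**5. Illustration of size, on assumed inputs.** Suppose that practice on the test were the only source of a between-arm difference, of d SDs in the compared quantity. The values of d are assumptions. Compare the arms by a t test with n = 10 per arm:

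- df = 10 + 10 − 2 = 18
- noncentrality = d × √(n/2) = d × √5 = 0.559, 1.118 and 1.677 for d = 0.25, 0.5 and 0.75
- The SAP corrects pairwise comparisons within each outcome by Bonferroni. Assuming two follow-up comparisons (EOT and EOT+4) and two-sided tests, alpha = 0.05/2 = 0.025 and the critical value is t = 2.445.

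| Assumed practice gain d | Chance of a significant result favouring DT, per comparison |
|---|---|
| 0 | 1.25% |
| 0.25 SD | 4.3% |
| 0.5 SD | 11.5% |
| 0.75 SD | 24.8% |

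These are rates before the SAP's requirement of a significant group-by-time interaction, which could only lower them. They are not type I error rates: for d above 0 there would be a true difference in cup-walk distance. They show only how often a difference specific to the test might be declared.

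**The case against.** **No document says that the cup walk will be trained.** This stands. Phase 1 gait testing, from which the training is to be derived, uses cognitive secondary tasks, so the eventual list may well omit cup-carrying. A reader might infer that the safeguard has failed or that the result is biased. The text shows only that the practice is permitted.

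**A gain from practising the walk is a treatment effect.** This also stands. The arms are randomised, the outcome is distance walked, and no passage calls the cup walk a test of transfer. A reader might infer an inflated false-positive rate. That does not follow, because a significant result would reflect a real difference in the measured quantity. What remains is how widely that difference may be interpreted.

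**A rule limited to cognitive tasks is coherent.** This stands in part. Cognitive tests have learnable formats, and a ban on every evaluated motor task would be unworkable because walking is both trained and tested. It does not explain leaving out the cup walk, which can be withheld without touching walking or other motor-motor training.

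**The reach is small.** This stands. It is one condition of a secondary outcome in a pilot, and no primary conclusion depends on it.

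**Conclusion.** The point holds as a limited gap. The rule against learning effects does not achieve its own stated purpose for the motor-motor 2MWT, and the only arm whose training could include that task is the DT arm. If the cup walk is trained, a DT advantage on that condition shows improvement on a practised task. It would not, by itself, support a claim of better dual-tasking in general.

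The conclusion rests on the wording of the rule, the two arm descriptions and Table 1. It does not rest on the illustrative percentages, whose practice gains and number of comparisons are assumed. Whether the gap matters in practice depends on the Phase 2 training protocol, which is not among the documents. It would be too strong to say that the dual-task findings as a whole are compromised, since the primary gait analysis and the serial-7 2MWT use cognitive tasks that the rule already keeps out of training.

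**What to change.** Extend the sentence in the Research Plan along these lines: *The cognitive tasks used for evaluation, and the secondary motor task used for evaluation (walking while holding a cup of water), will not be used during the intervention. Walking and other motor-motor tasks remain available for training.* Naming the specific task avoids any doubt about whether carrying tasks in general are barred.

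Add to the SAP that, if the cup walk is trained in any participant, this is recorded by arm and that 2MWT condition is reported as a trained-task result, not as evidence of a general dual-task gain.

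The cost is a few words in the protocol, one line in the SAP, and one training task that therapists cannot use. If Phase 2 training is already complete, the sentence can no longer prevent the practice. The remedy is then to establish from the training protocol and any session records whether the cup walk was used, and to word the report accordingly.

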The Effects of Dual Task Training on Motor and Non-Motor Function in Individuals with
Parkinson's Disease

NCT02538029

1.31.19

Statistical Analysis Plan

Phase 1:

Baseline participant demographics and outcome variables will be summarized by group using mean \pm standard deviation for normally distributed variables, median [25th percentile, 75th percentile] for data that is not normally distributed, or N (%) (categorical data). Paired sample t-tests will be used to detect differences in cognitive scores between single and dual-task conditions. A repeated measures analysis of variance (ANOVA) model will be used to determine the effects of the different cognitive dual tasks and single-task on gait performance as measured by the spatial-temporal parameters of gait. When the ANOVA model results in significant differences in comparison from single to dual-task, a post hoc pairwise comparison will be performed to identify which tasks were significantly different from each other. The p-values in multiple comparisons will be adjusted using the Bonferroni correction. All statistical testing will be performed at the 5% level of significance.

Phase 2:

Baseline participant demographics and outcome variables will be summarized by group using mean \pm standard deviation for normally distributed variables, median [25th percentile, 75th percentile] for data that is not normally distributed, or N (%) (categorical data). The intervention effects on outcomes will be assessed using separate linear mixed effects models, each including a random intercept, main effects for group, time, and a group-by-time interaction term. Given a significant group by time interaction, post hoc pairwise comparisons will be performed between groups at each follow-up. In the absence of a group-by-time interaction, the overall change across collapsed groups between each evaluation will be estimated (i.e., change from Baseline to End of Treatment and Baseline to End of Treatment + 4 weeks). All comparisons will be performed at the 0.05 significance level. Within each outcome, pairwise comparisons will be Bonferroni corrected to maintain a 5% type I error rate per outcome.

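### Does placing three of Aim 1's five cognitive domains on the N-back task alone call for a change to the Phase 1 plan?

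*Protocol*

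**What the plan says.** Aim 1 plans gait analysis while walking alone and while walking with tasks from five domains: "processing speed, visual memory, verbal memory, executive function, and attention (See Table 1 for cognitive tasks". In Table 1 the tasks carry these labels:

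- N-back: "Executive function, attention, and visual memory: participant is presented with a visual sequence of letters".
- Stroop: processing speed.
- Repeated digit sequence: verbal memory.
- Serial 7s and arithmetic: mathematical reasoning, which is not one of the five.
- Verbal fluency: a description of the task and no domain.

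The Research Plan says that Phase 1 interventions will be documented "in order to attribute changes in gait parameters of postural stability with a domain of cognitive function". The rationale gives two examples built on visual memory. One imagines gait changes "during visual memory cognitive tasks that are not seen during verbal memory cognitive tasks"; the other continues "if we find that visual memory tasks lead to decreased stride length, then the therapeutic intervention would be a task", naming targeted stepping as the therapy. For Phase 1 the SAP fits a repeated measures ANOVA for "the effects of the different cognitive dual tasks and single-task on gait performance", followed by Bonferroni-adjusted pairwise comparisons of tasks. On training content, the section on the DT clinical group says: "Cognitive tasks will include processing speed, attention, memory, cognitive flexibility, and executive function tasks".

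**The concern.** The stated purpose is attribution to a domain, but one task carries three domains. If gait worsens under N-back, the data cannot say which of the three is responsible. Both examples in the rationale turn on visual memory, and the only task labelled visual memory is N-back. Following either example literally would credit one domain with an effect that could come from any of three. Phase 1 is meant to inform Phase 2, so a misread N-back result could tilt the training towards visual memory without support. Expected Results also presents "insight to which DT constructs result in specific gait and postural control changes" as a hallmark finding that will guide clinicians, which raises the apparent stakes.

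**Working it through.** The plan gives no figure to reproduce. The check has two parts: what the labels allow, and whether any planned analysis uses them.

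**1. What the labels allow.** Assume, as the documents do not, that each domain adds a fixed amount to the change in gait from single-task walking and that a task carries exactly its printed domains. Write VM, VeM, PS, EF and AT for visual memory, verbal memory, processing speed, executive function and attention. Then:

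- Δ(N-back) = VM + EF + AT
- Δ(Stroop) = PS
- Δ(digit sequence) = VeM

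That is three independent equations in five unknowns (rank 3). PS and VeM are each estimable. VM, EF and AT are not; only their sum is. So 2 of 5 domains are separable as printed.

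The first example in the rationale becomes Δ(N-back) − Δ(digit sequence) = VM + EF + AT − VeM. This equals the visual-minus-verbal contrast only if EF + AT = 0.

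The count depends on labels that the documents do not print:

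| Assumed labels | Separable domains |
|---|---|
| As printed | 2 of 5 (PS, VeM) |
| Verbal fluency = EF | 3 of 5 (adds EF; VM + AT stay joint) |
| Verbal fluency = EF, serial 7s = AT | 5 of 5, with VM = Δ(N-back) − Δ(fluency) − Δ(serial 7s) |
| Stroop also carries EF and AT | 1 of 5 (VeM only) |

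The range of 1 to 5 comes entirely from the assumed mapping. It describes the labels and measures no error in the trial.

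**2. Whether a planned analysis uses the labels.**

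| Planned step | Unit compared | Uses a domain label? |
|---|---|---|
| Phase 1 paired t-tests (SAP) | cognitive scores, single against dual task | No |
| Phase 1 repeated measures ANOVA (SAP) | single task and each dual task | No |
| Phase 1 post hoc comparisons (SAP) | task against task | No |
| Phase 2 mixed models (SAP) | group, time and their interaction | No |

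None of the four uses a domain. Relabelling any row of Table 1 leaves every estimate, p-value and Bonferroni divisor as it was.

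**3. Whether Phase 2 training could go astray.** The protocol bases the training on gait analyses across dual-task conditions and says that interventions will be prioritised by the gait and postural deviations seen. The training list includes attention, memory and executive function, so none of the three N-back domains drops out whichever way an N-back effect is read. Only relative emphasis could shift.

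**The case for a change.** The best case for a change is that the analysis is by task, the declared conclusion is by domain, and no rule connects them. The rationale's examples are the only worked route from a Phase 1 result to a therapy task, and both use a domain that cannot be isolated. The protocol also keeps evaluation tasks out of the intervention, so a bare task-level result does not say what to train; some step through domains is needed. The repair would cost only words.

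Part of this stands. An N-back effect should not be called a visual-memory effect, and the labels for verbal fluency and serial 7s are incomplete.

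The rest is weaker. Both examples are conditional and sit in the rationale; neither is a decision rule. The domain-attribution sentence concerns documentation and has no estimand or test attached. The hallmark statement is poor evidence, because the protocol mostly uses that term for single- or dual-task conditions. The obvious repair, reporting N-back as a joint effect of three domains, would itself mislead: it suggests that all three contribute, when the data show only that the task changed gait. Nor does a single printed label prove that Stroop or the digit sequence draws on one domain alone. Table 1's column describes functions evaluated and is not shown to be a complete domain map.

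**Conclusion.** No change to the plan is needed. Three of the five Aim 1 domains share one task, so Phase 1 cannot separate them; this rests on the labels as printed and on the additive assumption used in the check. The effect on planned tests, error rates and sample size is nil, because every SAP comparison is made by task, group or time. Using a multi-domain task in a 15-person characterisation phase is a fair design choice. The missing link from task to domain is a gap that analysts fill sensibly by naming the N-back result as an N-back result, attributing it to no single domain and not implying that all three are at work. The absent Aim 1 labels for verbal fluency and serial 7s are missing detail that alters no planned result.
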